### **5.2. Data to be collected specifically for VIOLET-BUD (Table 1)**

The primary outcomes for VIOLET-BUD are long-term global cognition and executive function. Only patients who have LC-MS confirmed Vitamin D deficiency (plasma 25-OHD < 20 ng/dL) at enrollment will have their outcomes determined. All outcome assessments will be blinded to treatment group. We will use comprehensive neuropsychological assessment which allows for detailed evaluation of specific cognitive domains. Prior work suggests Vitamin D deficiency predominantly affects short-term and working memory, attention, and executive function.

Long-term global cognition will be assessed for using the ***Repeatable Battery for the Assessment of Neuropsychological Status (RBANS, 30 min, Appendix C)***, which we have extensively used in our prior work. The RBANS is a comprehensive neuropsychological battery for the evaluation of global cognition and has been validated in subjects with mild cognitive impairment, moderate to severe traumatic brain injuries, vascular dementias, and Alzheimer's disease. In addition to providing a score for global cognition, it also provides individual scores for immediate and delayed memory, attention, visuospatial construction, and language.

To quantify executive function, we will use tests from the ***Delis-Kaplan Executive Function System (D-KEFS)*** which is the most definitive executive functioning battery in existence. Executive functioning refers to a wide array of "higher order" abilities that exist across a spectrum of cognitive sub-domains. Recent factor analyses have suggested that the majority of executive sub-domains fall broadly under conceptual flexibility, inhibition, and monitoring. As such, we have selected tests of executive functioning from the D-KEFS to assess these three broad abilities – ***the DKEFS Proverbs subscale (conceptual flexibility, 5 min, Appendix D), the DKEFS Trail Making-Number/Letter Switching subscale (inhibition, 2 min, Appendix E), and DKEFS Verbal Fluency Category Switching subscale (monitoring, 3 min, Appendix F)***. An executive function composite score will be calculated from these three DKEFS subscales.

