## **9.0 Statistical Considerations**

We will determine if single, high-dose enteral Vitamin D treatment improves long-term global cognition and executive function compared with placebo using multiple linear regression. One model will be constructed for long-term RBANS and another for long-term executive function. We will use multivariable linear regression over unadjusted analyses because it is hypothesized that there will be a 5% absolute risk reduction in death for those who receive enteral Vitamin D. This may imbalance potential confounders between the treatment and placebo groups. Additional imbalances may

occur because of random chance. Multivariable regression will minimize this bias and lead to moderate gains in power.

The models will be adjusted for the covariates listed in **Table 2**. Nonlinear predictor effects for continuous variables will be incorporated into the models. If necessary, non-normally distributed continuous variables will be transformed. To account for correlation within a center, we will use robust standard errors.

In the event of significant missing covariate data, *multiple imputation* will be considered.

Multiple imputation will also be performed if portions of the cognitive assessments are missing; patients with completely missing cognitive data will be excluded from the study. Because several of our covariates (e.g., premorbid cognition and intelligence) may be highly correlated, we will assess for collinearity using variance inflation factors and use only one of those variables if a high degree of collinearity is observed. The final models will be validated using bootstrap internal validation and cross validation approaches. After the initial analysis has been completed, we will also evaluate if there is any effect modification of age, dementia status (medical record), baseline severity of illness (SOFA), mechanical ventilation status, and ARDS status. We will also perform a sensitivity analysis where death within the follow-up window will be considered equivalent to the worst cognitive outcome. This will be performed to further determine the effect of death on our findings.

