### 3. Study Population

VIOLET-BUD enrolled subjects from November 2018 to October 2019 in 7 (out of 42) PETAL sites that participated in VIOLET. The local site contacted all patients who were enrolled in VIOLET to recruit patients for VIOLET-BUD. Originally, the objective was to conduct the follow-up assessments 12  $\pm$  4 months after randomization. Due to slower than anticipated enrollment, VIOLET-BUD expanded the follow-up window from 12 months to include all survivors. The median (interquartile range) time from randomization to follow-up was 443 (386.5, 481.5) days.

Patients were excluded from VIOLET-BUD if they were deaf, blind, or non-English speaking. Patients who were deaf or blind were excluded, because the neuropsychological testing has auditory and visual components. Non-English speaking patients were excluded because the neuropsychological raters can only perform the assessments in English.

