To determine if single, high-dose enteral Vitamin D treatment improves long-term global cognition and executive function compared with placebo, we will use multivariable linear regression or proportional odds logistic regression models based on the distribution of the continuous outcomes (**Figure 1**). Separate models will be constructed for long-term RBANS and executive function and adjusted for the baseline covariates listed in **Table 2**. Post-randomization covariates (e.g., interventions provided during hospitalization) will not be adjusted for because they may potentially be affected by the randomized intervention and be on the causal pathway. Prior to modeling, we will perform redundancy analyses to ensure that no covariates completely explain any of the others (resulting in multicollinearity) using an adjusted  $R^2$  cutoff of 0.7. If any covariates are highly correlated, only one of them based on clinical relevance will be kept in the model. If the multivariable models do not converge due to limited variability or low number of patients in specific levels of certain covariates, the number of covariates will be reduced based on the least rank in the order specified above. Restricted cubic splines for continuous variables will be incorporated into the models based on the distribution. To account for correlation among patients within a given site, we will adjust standard errors using Huber-White sandwich estimate. Partially missing long-term outcomes will be imputed using single imputation.

As exploratory heterogeneity of treatment effect analyses for primary outcomes, we will evaluate for effect modification by age, pre-existing cognitive impairment (e.g., dementia), baseline severity of illness (Sequential Organ Failure Assessment), infection (pneumonia or sepsis diagnosis), and pre-morbid intelligence (Barona). Because this is an exploratory analysis, we will consider an interaction term p-value less than 0.20 to suggest the potential presence of effect modification.

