## D5.2. Sample Size Calculations

In our original sample size calculations, we used half a standard deviation (SD) of that particular test to define the minimum clinically important difference (MCID) threshold. The SD for the RBANS in our population from previous studies was 12.4. Thus, we considered a 6-point difference to be the MCID threshold for the RBANS. Based upon a two-sided alpha of 0.05 and 80% power, we computed that we would need outcome data in a total of 140 patients with completed follow-up data (~70 patients in each group) to detect a 6-point difference in RBANS between treatment groups. However, VIOLET-BUD enrolled 95 patients; because the VIOLET parent trial stopped enrollment early, no additional patients could be recruited for this ancillary study. However, this sample size still provides us with more than 80% power to detect at least a

7.2-point difference. Some have considered an RBANS difference of 8 points to be the MCID threshold. For our executive function composite score, the SD in our previous population was 2.34. With 95 patients assessed, we will have greater than 80% power to detect a 1.4-point difference in the executive function composite score assuming a two-sided alpha of 0.05.

For our multiple linear regression models, we will have one degree of freedom available for every 10 to 15 patients with completed outcome measurements. Consequently, we will be able to accommodate 9 degrees of freedom for our multivariable models without overfitting.

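### SAP 5.2 replaces the protocol's multiple imputation of partly missing primary outcomes with an unnamed single imputation and gives no reason; the effect is probably small and is cheap to remove

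*SAP*

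**What the plan says.** Protocol 9.0 treats missing covariates and missing outcomes differently. For covariates, multiple imputation is only to be considered ("In the event of significant missing covariate data"). For outcomes the commitment is firm: "Multiple imputation will also be performed if portions of the cognitive assessments are missing". The limit is also stated: "patients with completely missing cognitive data will be excluded from the study".

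SAP 5.2 has one sentence on the subject: "Partially missing long-term outcomes will be imputed using single imputation". It does not say whether the method is mean, regression, hot-deck or proration, which predictors enter, whether treatment is one of them, or whether components or totals are imputed. No multiple-imputation sensitivity analysis is planned.

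The only variance adjustment is for site: "To account for correlation among patients within a given site, we will adjust standard errors using Huber-White sandwich estimate".

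Both primary outcomes are built from parts. RBANS has five domains. For the D-KEFS tests, Protocol 5.2 says: "An executive function composite score will be calculated from these three DKEFS subscales".

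The SAP was written after follow-up. Section 3 reports "The median (interquartile range) time from randomization to follow-up was 443 (386.5, 481.5) days", and section D5.2 reports "However, VIOLET-BUD enrolled 95 patients" against a target of 140.

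**The concern.** A SAP may refine a protocol, but a refinement adds detail. Here a named method gives way to an unnamed one, in the adjusted analyses that SAP section 5 makes primary.

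The candidate methods fail in different ways. Regression-based single imputation, with or without a random residual, treats imputed components as data, so standard errors and 95% intervals come out too small. Mean imputation pulls the treatment effect toward zero. Proration (averaging the patient's observed components) may do neither. A reader cannot tell which applies. Interval width matters here because the SAP says its reporting will put effect sizes and intervals ahead of significance.

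Partial scores are foreseen: Protocol 6.0 lets staff skip a task or end testing if the patient is distressed.

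**Working it through.** **Inputs from the documents.** N = 95 and 7 sites (SAP D5.2, SAP 3). SDs 12.4 for RBANS and 2.34 for the composite (SAP D5.2). Five RBANS domains and three D-KEFS subscales. Model with 9 df (SAP Table 2), so residual df = 95 - 1 - 9 = 85.

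**Assumed, because the documents are silent.** Share of partial scores 5, 10, 20 or 30% (5, 10, 19 or 28 of 95 patients); one or two components missing, completely at random; correlation between components 0.4 or 0.6; equal weights; about 47.5 patients per arm.

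**1. The SAP's own figures.** SE of a difference = SD x sqrt(2/47.5).
- RBANS: 12.4 x 0.2052 = 2.544. Then 7.2/2.544 = 2.830, and power = Phi(2.830 - 1.960) = 80.8% (80.0% by noncentral t).
- Composite: 2.34 x 0.2052 = 0.480. Then 1.4/0.480 = 2.916, and power = 83.0% (82.3% by noncentral t).

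These agree with the SAP, assume complete data and are not in dispute.

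**2. Regression-based single imputation.** Simulation with 20,000 null trials per setting. SE shortfall = 1 - (mean SE / empirical SD), relative to the same ratio with complete data. The Monte Carlo margin is about 0.5 points on the shortfall and 0.3 on type I error.

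| Partial scores | Composite, 1 or 2 of 3 missing | RBANS, 1 or 2 of 5 missing |
|---|---|---|
| 5% | 0.8-2.8% | 0.2-1.2% |
| 10% | 1.3-5.7% | 0.4-2.2% |
| 20% | 2.7-11.1% | 0.8-4.4% |
| 30% | 4.3-16.6% | 1.5-6.8% |

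The table uses heteroscedasticity-robust (HC2) errors; with a site-clustered sandwich the shortfall is almost the same. Type I error with the clustered sandwich and t on 6 df, at 10% partial, is 5.1-5.9% (composite) and 4.9-5.7% (RBANS), against 4.7-5.2% with complete data.

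A second simulation (3,000 trials, one covariate, correlation 0.3 or 0.6, deterministic regression) agrees at 10% partial. For the composite, the extremes are 1 - 0.989/1.000 = 1.1% and 1 - 0.946/0.996 = 5.0%. For RBANS with one domain missing they are 1 - 1.002/1.007 = 0.5% and 1 - 0.977/0.987 = 1.0%.

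**3. The same in points, at 10% partial.** The 95% half-width is t x SE x sqrt(1 - R2), with t = 1.988 (85 df) and R2 from 0 to 0.3.
- RBANS: 1.988 x 2.544 = 5.1, down to 5.1 x 0.837 = 4.2. Understated by 0.4% x 4.2 = 0.02 to 2.2% x 5.1 = 0.11 points.
- Composite: 1.988 x 0.480 = 0.95, down to 0.80. Understated by 1.3% x 0.80 = 0.01 to 5.7% x 0.95 = 0.05 points.

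**4. Mean imputation.** Shrinkage = (share partial) x (components missing / components). At 10/95:
- Composite: 0.1053 x 1/3 = 3.5%; 0.1053 x 2/3 = 7.0%. On a 1.17-point effect that is 0.04-0.08 points.
- RBANS: 0.1053 x 1/5 = 2.1%; 0.1053 x 2/5 = 4.2%. On a 6-point effect that is 0.13-0.25 points.

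The SE was within 0.5% of correct and type I error was 4.7-5.4%.

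**5. Proration.** SE within 0.4% of correct, type I error 4.8-5.4%, no shrinkage when all components carry the same effect.

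**6. Multiple imputation (20 imputations, Rubin's rules).** With HC2 errors, the SE ran from 0.1% too small to 1.5% too large, and type I error was 4.5-5.4%. With the clustered sandwich at 10% partial, type I error was 3.7-4.8% on t with 6 df, or 2.4-3.7% on Rubin's small-sample df. The choice of reference distribution therefore matters.

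Not simulated: the proportional odds alternative in SAP 5.2, and a patient with one battery wholly missing.

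**The case against.** The strongest reply is that the harm is conditional and small. Only one family of methods gives short standard errors, and proration has neither fault. At 10% partial the RBANS interval changes by about a tenth of a point at most. The upper ends need every partial patient to lose two components. Protocol 6.0 allows rest and rescheduling, and Protocol 5.2 trains proctors to give portions of the tests if the connection fails, so partial scores should be few. All of this stands and sets the weight of the point.

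Multiple imputation also has a cost: with seven sites the pooled clustered test is conservative, and under Rubin's small-sample df it lies further from 5% than single imputation does. That stands too, and it is why the fix must name the reference distribution.

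A reader might infer that false-positive rates are seriously inflated. With HC2 errors and 30% partial scores, simulated type I error for the composite does reach 10.1%. But nothing in the documents supports such a share, and HC2 does not account for the within-site correlation that the SAP's sandwich is meant to handle.

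A reader might also infer that the method was changed after results were seen. The documents show only that follow-up was complete; they do not say whether unblinded outcomes had been examined. Nor is the silence distinctive: the SAP also drops the Charlson covariate and the bootstrap validation without a specific reason.

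What remains is that a firm commitment on both primary outcomes was replaced by a phrase that does not identify an analysis.

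**Conclusion.** The discrepancy is certain, since it is in the current text of both documents. Its size is not, because the share of partial scores, the correlation between components and the method itself are all unstated. Under the assumptions above, the distortion is larger for the three-part composite than for RBANS and close to nil for RBANS with one domain missing. It could change a conclusion only for a result near the 5% boundary. This is a cheap improvement; it does not show that the primary analyses are invalid.

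**What to change.** Replace the SAP sentence with:

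> Partially missing RBANS and D-KEFS component scores will be multiply imputed (20 or more imputations) from treatment, the Table 2 covariates (linear terms) and the patient's observed components. Each completed data set will be analysed with the planned model and site-clustered standard errors. Results will be combined by Rubin's rules, with tests and intervals referred to a t distribution with 6 df (7 sites minus 1).

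Linear terms keep the imputation model small. With the observed components of the same battery it has 7-8 predictors for the composite and 9-10 for RBANS.

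The SAP should also say what happens to a patient with one battery wholly missing. The protocol excludes only patients with no cognitive data at all, so on its wording this patient is imputed. Leaving the patient out of that outcome's model is possible, but it narrows the protocol and should be declared as such.

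If single imputation is kept, name the method and give the reason. Counts of partial scores by arm belong in the results.

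**Cost.** One sentence and a few lines of code, with no new data. At 10% partial, intervals are wider than under regression-based single imputation by about 1.0-6.5% (composite) and 0.4-2.5% (RBANS), and the test is slightly conservative with seven sites.

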### 4. Variables Collected for VIOLET-BUD

#### 4.1 Primary Outcome Variables

The primary outcomes for VIOLET-BUD are long-term global cognition and executive function, as determined by a comprehensive neuropsychological assessment. Global cognition was assessed for using the ***Repeatable Battery for the Assessment of Neuropsychological Status (RBANS)***. The RBANS is a comprehensive neuropsychological battery for the evaluation of global cognition and has been validated in subjects with mild cognitive impairment, moderate to severe traumatic brain injuries, vascular dementias, and Alzheimer's disease. In addition to providing a score for global cognition, it also provides individual scores for immediate and delayed memory, attention, visuospatial construction, and language.

To quantify executive function, we used tests from the ***Delis–Kaplan Executive Function System (D-KEFS)***. An executive function composite score was calculated using scores from the ***DKEFS Proverbs, Trail Making-Number/Letter Switching, and Verbal Fluency Category Switching subscales***.

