To determine how time to neuropsychological assessment impacted our findings, we will also conduct a sensitivity analysis; we will re-run the multivariable regression models adjusting for time to neuropsychological assessment. Patients were included in VIOLET (and VIOLET-BUD) if their plasma Vitamin D concentrations were < 20 mg/dL as determined by local immunoassay (clinical laboratory or point-of-care) testing. The VIOLET parent trial also confirmed baseline (pre-randomization) Vitamin D deficiency using liquid chromatography-mass spectrometry (LC-MS), the gold standard for Vitamin D measurement, conducted at the University of Washington on batched samples after 90-day follow-up was completed. VIOLET-BUD's primary analyses will use immunoassay Vitamin D measurements. We will re-run the multivariable regression models and adjust for baseline Vitamin D levels as measured by LC-MS as a sensitivity analysis. Because the VIOLET parent study did not observe a significant difference in 90-day mortality between the Vitamin D and placebo groups, analyses accounting for differential mortality will not be performed.

Other secondary analyses will include associations between Vitamin D treatment and individual RBANS cognitive domains (e.g., immediate and delayed memory, attention, visuospatial construction, and language) and executive function subscales (DKEFS Proverbs, Trail Making-Number/Letter Switching, and Verbal Fluency Category Switching). We will also determine if treatment is associated with functional status (Katz and Lawton).

Level of statistical significance will be set at 5%. All tests will be two-sided and 95% confidence intervals will be reported along with all effect estimates. Presentation of results will emphasize clinical significance, effect sizes, and confidence intervals, over statistical significance. Regarding the analyses of all *a priori*-defined secondary outcomes described herein, no adjustments will be made for multiple comparisons in keeping with recommendations on this topic and standard practice when analyzing multiple, prospectively defined outcomes in a clinical trial.

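### Interaction p-values below 0.20 are read as possible effect modification across 10 tests, so about two chance flags are expected, and the seven-site sandwich standard error is likely to add more

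*SAP*

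**What the plan says.** SAP section 5.2 introduces the analyses with "As exploratory heterogeneity of treatment effect analyses for primary outcomes" and continues "we will evaluate for effect modification by age, pre-existing cognitive impairment (e.g., dementia), baseline severity of illness" (SOFA), then adds infection and Barona-estimated intelligence, five modifiers in all. Section 4.1 names two outcomes: "The primary outcomes for VIOLET-BUD are long-term global cognition and executive function". The reading rule is "we will consider an interaction term p-value less than 0.20 to suggest the potential presence of effect modification".

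The same section accounts for correlation within sites by a Huber-White sandwich estimate and states no small-sample correction. Section 3 gives 7 sites. Section 5.2 also says "All tests will be two-sided and 95% confidence intervals will be reported along with all effect estimates" and "Presentation of results will emphasize clinical significance, effect sizes, and confidence intervals, over statistical significance". Its statement that multiple comparisons will not be adjusted for is limited to pre-defined secondary outcomes, so it does not cover interactions on the primary outcomes. The SAP gives no expected number of chance flags and no rule for reporting a flag. Protocol section 9.0 plans effect-modification analyses with a partly different list of modifiers and sets no p-value threshold.

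**The concern.** A screen is useful if a flag is clearly more likely when effect modification exists than when it does not. Ten tests at 0.20 return flags in most trials with no effect modification at all, and the SAP does not tell the reader so.

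The standard error is a second problem. A cluster sandwich built from seven sites tends to be too small, more so for a coefficient that rests on a handful of patients. The false-flag rate is then above the 20% that the SAP appears to have chosen. With 95 patients, an interaction that passes the screen can also be numerically large. A chance result may therefore be read as a subgroup that benefits from, or is harmed by, vitamin D.

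**Working it through.** **Inputs.** Five modifiers, threshold 0.20, 7 sites (SAP 5.2 and 3); two primary outcomes (SAP 4.1); 95 patients, RBANS SD 12.4, 6-point minimum clinically important difference (MCID), executive function SD 2.34 (SAP D5.2); executive function MCID 1.17 and 1:1 allocation stratified by hospital (Protocol 9.0 and 4.0). The documents do not give the correlation between outcomes, modifier prevalence, variance explained by covariates, or patients per site. These are assumed below and shown as ranges.

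**The SAP's own figure.** The SE of the treatment effect with 47 and 48 patients is 12.4 × √(1/47 + 1/48) = 2.54. For 7.2 points, 7.2/2.54 − 1.96 = 0.87, which gives 80.8% power (80.0% with the t distribution). This agrees with SAP D5.2. The SAP states no error rate for the interaction rule.

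**Flags expected by chance, correctly sized tests.** There are 5 × 2 = 10 tests, and 10 × 0.20 = 2.0 flags are expected at any correlation. For the chance of at least one, test statistics are treated as independent across modifiers and correlated between the two outcomes within a modifier:

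| Between-outcome correlation | P(at least one flag) |
|---|---|
| 0 | 1 − 0.8^10 = 89.3% |
| 0.5 | 86.9% |
| 0.7 | 83.9% |
| 0.9 | 78.2% |
| 1 | 1 − 0.8^5 = 67.2% |

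The chance of two or more is about 59% to 62%. At a 0.05 threshold, 0.5 flags would be expected and 1 − 0.95^10 = 40.1% of trials would have at least one (independent tests).

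**Is the 20% level kept?** Trials with 95 patients, 7 sites of assumed size and no true interaction were simulated under several settings, using a site-clustered sandwich without small-sample correction:

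- In one setting, 30–36% of tests were flagged, and 39–50% for a rare pre-existing impairment.
- In another, the rates were 31–32% for infection and 47–50% for age, SOFA and Barona. For pre-existing impairment they were 39% with 10 affected patients and 57% with 4 (both numbers assumed). At least one flag for a single outcome occurred in 94–96% of trials.
- In a third, about 3.4 of 10 tests were flagged, and 97% of trials had at least one (correlation 0.7).
- With model-based SEs the rate was about 20% per test, and 67–68% for at least one of five.

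The settings disagree on the size of the inflation but not on its direction.

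**How large is a false flag?** For a two-level modifier with prevalence q, SE = SD × √(4/(Nq) + 4/(N(1−q))). At q = 0.5 this is 12.4 × √(4/23.75) × √2 / √2 = 12.4 × √(4/23.75) = 5.09, since each of the four cells holds 95/4 = 23.75 patients. For a continuous modifier, per SD, SE = 2 × 12.4/√95 = 2.54. A two-sided p below 0.20 needs about 1.29 SEs (t, about 85 df). The smallest flagged RBANS difference in a correctly sized test is:

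| Modifier | Covariates explain 0% of variance | 30% |
|---|---|---|
| Two-level, 50:50 | 6.6 | 5.5 |
| Two-level, 10% | 11.0 | 9.2 |
| Continuous, per SD | 3.3 | 2.8 |
| Continuous, −1 to +1 SD | 6.6 | 5.5 |

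For executive function, 50:50, the values are 1.24 and 1.04, against an MCID of 1.17. If the sandwich SE is too small, flags occur at smaller differences: a 31% flag rate corresponds to a cutoff of roughly 1.0 × 5.1 = 5.1 points for a 50:50 modifier.

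**The case against.** The SAP calls these analyses exploratory and speaks only of a potential presence. No decision follows from a flag. A liberal threshold is a recognised trade-off: with SE 5.09, power for a true 6-point interaction is about 22% at 0.05 and 47% at 0.20. Confidence intervals are already required, and with correctly sized one-df tests 0.15/0.20 = 75% of false flags would have a 95% interval that includes zero. The sandwich problem is not created by the 0.20 rule.

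Much of this stands. A screen at 0.20 is defensible if its yield is disclosed, and preferring estimates over significance does not forbid a p-value, so there is no outright contradiction within section 5.2. Two things remain. A flag is only 47/20 = 2.35 times as likely under a 6-point interaction as under none, and the SAP does not help the reader allow for that. The trade-off also assumes a 20% error rate that the specified standard error probably does not deliver.

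A reader might go further and infer that every flag would look clinically large. The table does not support this. With covariate adjustment a 50:50 modifier can be flagged below 6 points. For age, SOFA and Barona the size depends on the contrast shown. The SAP also mentions an 8-point MCID, which a flagged difference for a balanced modifier need not reach.

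**Conclusion.** The concern holds as an error-rate and reporting defect in exploratory analyses. With correctly sized tests and no true interaction, about two of 10 tests are flagged, with a 78–89% chance of at least one (67% if the outcomes were perfectly correlated). With the sandwich SE on seven sites the rate per test is roughly 30–57%, highest for a rare modifier. That range rests on assumed site sizes and prevalences, on reading the SAP's estimator as clustered by site, and on no correction being applied. A false flag would often reach the 6-point MCID, mainly for uncommon two-level modifiers.

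A reader might infer that a subgroup finding is all but guaranteed, or is this study's likeliest positive message. The first needs the assumed simulation settings, since the document-based figure is 78–89%. The second is speculation, because the parent trial's mortality result says nothing about cognition. The 0.20 rule does not touch the primary treatment comparison. Whether the same standard error suits that comparison is a separate question.

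**What to change.** For the interaction analyses in SAP 5.2:

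- Replace the uncorrected seven-site sandwich with model-based SEs, adding site as a covariate if wanted, or with a small-sample-corrected cluster SE whose behaviour is checked for rare modifiers.
- Report all 10 interactions as differences in treatment effect between stated values of the modifier, with 95% confidence intervals (on the odds-ratio scale if a proportional odds model is used), instead of labelling them by p below 0.20.
- If the 0.20 screen is kept, state beside the results that 10 tests were done, that about 2 flags are expected by chance, and that no effect modification is claimed. The figure of 2 is valid only once the SE is corrected.
- Give the pre-existing impairment interaction descriptively if very few patients have the condition.

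The cost is SAP wording and a re-specified SE. Site as a covariate would use 7 − 1 = 6 further degrees of freedom, and Table 2 of the SAP already uses its full 9. Model-based SEs without site would drop the SAP's handling of within-site correlation for these tests. Fewer exploratory leads would be labelled, but every estimate stays visible.
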